### **10.3 Objection by minors or incapacitated subjects (if applicable)**

Not applicable

### **10.4 Benefits and risks assessment, group relatedness**

All patients enrolled in this trial will receive the maximum vascular, endovascular or conservative (antibiotics, anticoagulants, glycaemic control) and local wound treatment according to best practice. The possible effect of adding HBOT tot the standard treatment may result in major benefits such as an improved limb salvage and higher wound healing rates. HBOT is regarded as a low-risk therapy.

### **10.5 Compensation for injury**

The sponsor/investigator has a liability insurance which is in accordance with article 7 of the WMO. The sponsor (also) has an insurance which is in accordance with the legal requirements in the Netherlands (Article 7 WMO). This insurance provides cover for damage to research subjects through injury or death caused by the study.

The insurance applies to the damage that becomes apparent during the study or within 4 years after the end of the study.

### **10.6 Incentives (if applicable)**

All Dutch recruiting centers receive 100 euro for each patient that completes the 12-month follow-up period (and data are recorded completely) as a compensation for their effort.

## **11. ADMINISTRATIVE ASPECTS, MONITORING AND PUBLICATION**

### **11.1 Handling and storage of data and documents**

All patient data will be stored in an eCRF in Castor, including a unique study number which will be allocated to each patient. This number identifies the patient and must be reported on all web-based case forms and questionnaires. The handling of personal data will be according to the EU General Data Protection Regulation and the Dutch Act on Implementation of the General Data Protection Regulation (in Dutch: Uitvoeringswet AVG, UAVG). Patient data will only be available to the principal and coordinating investigators. The data will be stored for 15 years.

### **11.2 Monitoring and Quality Assurance**

This study will be monitored following the current guidelines. Also, a DSMB is composed (see chapter 8.5). A full monitoring plan will be sent as soon as the funding for this study is obtained. A DSMB charter is added as attachment L5.

### **11.3 Amendments**

A 'substantial amendment' is defined as an amendment to the terms of the METC application, or to the protocol or any other supporting documentation, that is likely to affect to a significant degree:

- the safety or physical or mental integrity of the subjects of the trial;
- the scientific value of the trial;
- the conduct or management of the trial; or
- the quality or safety of any intervention used in the trial.

All substantial amendments will be notified to the METC and to the competent authority.

Non-substantial amendments will not be notified to the accredited METC and the competent authority, but will be recorded and filed by the sponsor.

### **11.4 Annual progress report**

The sponsor/investigator will submit a summary of the progress of the trial to the accredited METC once a year. Information will be provided on the date of inclusion of the first subject, numbers of subjects included and numbers of subjects that have completed the trial, serious adverse events/ serious adverse reactions, other problems, and amendments.

**11.5 Temporary halt and (prematurely) end of study report**

The sponsor will notify the accredited METC and the competent authority of the end of the study within a period of 90 days. The end of the study is defined as the last patient's last visit.

The sponsor will notify the METC immediately of a temporary halt of the study, including the reason of such an action.

In case the study is ended prematurely, the sponsor will notify the accredited METC and the competent authority within 15 days, including the reasons for the premature termination.

Within one year after the end of the study, the investigator/sponsor will submit a final study report with the results of the study, including any publications/abstracts of the study, to the accredited METC and the Competent Authority.

**11.6 Public disclosure and publication policy**

At least one full scientific article will be prepared by the coordinating and principal investigators. All local investigators will be acknowledged in the final manuscript when they include any number of patients. Co-authorship will be granted if they comply with the ICMJE guidelines.

The study results will be presented at national and international meetings by the coordinating and/or principal investigator. The subsets of data from each individual contributing center may be used for quality improvement purposes by the local investigator(s).

## 12. STRUCTURED RISK ANALYSIS

### 12.1 Potential issues of concern

#### a. Level of knowledge about mechanism of action

There is a high level of knowledge regarding the working mechanisms of HBOT. It has a variety of mechanisms of action: it improves tissue oxygenation; inhibits the pro-inflammatory reaction by reducing cytokines; improves neo-vascularization; has a bacteriostatic effect on anaerobic bacteria and stimulates stem cells and growth factors (Camporesi 2014).

#### b. Previous exposure of human beings with the test product(s) and/or products with a similar biological mechanism

HBOT is widely used and implemented for 13 different indications (Weaver 2014)

#### c. Can the primary or secondary mechanism be induced in animals and/or in ex-vivo human cell material?

The therapy does not target specific cells, but achieves its effect by an increased pO2.

#### d. Selectivity of the mechanism to target tissue in animals and/or human beings

The therapy does not target specific cells, but achieves its effect by an increased pO2.

#### e. Analysis of potential effect

See appendices D1. HBOT can cause sinus or middle ear barotrauma, myopia or an epileptic attack. Very high doses of HBOT over a prolonged period can cause central nervous system symptoms and pulmonary oxygen toxicity, which in very rare cases can be fatal (Camporesi 2014). The doses used in this study are much lower, in accordance with the SmPC (appendix D1), and widely implemented.

#### f. Pharmacokinetic considerations

See attachments D1.

#### g. Study population

Patients with ischemic DFUs will be included. Patients with pregnancy will be excluded.

#### h. Interaction with other products

Also see appendices D1. Pulmonary toxicity of bleomycine, amiodarone, furadantine (and similar antibiotics) can be increased by high doses of oxygen. Patients using these drugs are excluded from participation.

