### **4.3 Exclusion criteria**

A potential subject who meets any of the following criteria will be excluded from participation in this study:

1. Chronic Obstructive Pulmonary Disease (COPD) GOLD IV
2. Treatment with chemotherapy, immunosuppressive drugs or systemic corticosteroids within last 3 months, as this interferes with normal wound healing
3. End-stage renal disease requiring dialysis
4. Metastasized malignancy
5. Left ventricular failure with ejection fraction (EF) <20% or external pacemaker
6. Pregnancy
7. Insufficient proficiency of local language/English, or inability to complete the questionnaires

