**5.2 Use of co-intervention (if applicable)**

HBOT will be given in addition to standard care according to local best practice in expertise centers and will not intervene with the usual care. Although (vascular) interventions are preferably performed before the start of HBOT, participation in the study will not influence any additional interventions that might be needed during follow-up ((endo)vascular interventions, amputations, wound debridement, medication, etc).

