#### i. Predictability of effect

There is no biomarker to predict the effect of HBOT. A forefoot Transcutaneous PO2 measurement could be used to predict the changes of successful treatment (Fife 2002).

j. Can effects be managed?

There is no direct antidote or antagonist. When a patient shows signs of pulmonary toxicity or has an epileptic attack, the treatment will be immediately stopped. For barotrauma an ENT specialist will be consulted, who might place eardrum tubes if necessary.

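### Section 12.1h excludes users of amiodarone and furadantine-type antibiotics on lung-safety grounds, but no criterion in section 4.3 does, so a site screening from 4.3 alone could randomise them

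*Protocol*

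**What the plan says.** The structured risk analysis, section 12.1h, names an interaction: "Pulmonary toxicity of bleomycine, amiodarone, furadantine (and similar antibiotics) can be increased by high doses of oxygen". It follows this with an unqualified eligibility statement: "Patients using these drugs are excluded from participation".

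The list that governs entry is in section 4.3, introduced by "A potential subject who meets any of the following criteria will be excluded from participation in this study". Seven criteria follow. Only the second concerns medication: "Treatment with chemotherapy, immunosuppressive drugs or systemic corticosteroids within last 3 months". The reason given there is interference with wound healing. The six inclusion criteria in section 4.2 do not mention medication.

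Section 5.2, on co-interventions, says that "participation in the study will not influence any additional interventions that might be needed during follow-up", and gives medication as one of its examples.

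The risk analysis contains one other exclusion, in 12.1g: "Patients with pregnancy will be excluded". That one does appear in 4.3, as criterion 6.

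**The concern.** The protocol gives two different accounts of who may enter. Under chapter 4, a patient taking amiodarone or a furadantine-type antibiotic who meets the other criteria is eligible. Under chapter 12, the same patient is excluded because of a lung hazard from the trial treatment.

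Investigators can be expected to screen from the numbered criteria in chapter 4 rather than from a risk analysis at the back of the protocol. Section 4.3 does not refer the reader to chapter 12 or to attachment D1. Two things are at stake:

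- **Safety.** The risk analysis relies on this exclusion as its control for the interaction. If the exclusion is not applied at entry, that control is absent. A patient admitted this way could be allocated to HBOT, which is given in three of the four arms.
- **Consistency of the population.** The trial is multinational and stratified by centre. Sites working from different sections could apply different entry rules.

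**Working it through.** No arithmetic beyond counting applies. The check compares each drug group named in 12.1h with every entry criterion, then looks for any other text that closes the gap.

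**Inputs.** Three drug groups from 12.1h: bleomycin, amiodarone, and furadantine with similar antibiotics. Six inclusion criteria from 4.2 and seven exclusion criteria from 4.3, so 6 + 7 = 13 criteria.

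**Inclusion criteria (4.2).** These cover diabetes type, ulcer grade and duration, ischaemia thresholds, arterial imaging, adulthood and consent. None concerns medication.

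**Exclusion criteria (4.3), one by one.**

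| Criterion in 4.3 | Bleomycin | Amiodarone | Furadantine-type antibiotics |
|---|---|---|---|
| 1. COPD, GOLD IV | no | no | no |
| 2. Chemotherapy, immunosuppressives or systemic corticosteroids, last 3 months | yes, by class | no | no |
| 3. Dialysis-dependent renal disease | no | no | no |
| 4. Metastatic cancer | no | no | no |
| 5. Ejection fraction below 20%, or external pacemaker | no | no | no |
| 6. Pregnancy | no | no | no |
| 7. Language or questionnaire barriers | no | no | no |

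Criterion 1 concerns the lung, but as a disease and not as a drug exposure. Criterion 5 may exclude some patients who happen to take amiodarone, but only because of their cardiac function or pacemaker. It does not exclude amiodarone users as such.

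**Result.**

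- Bleomycin: 0 of 13 criteria by name, 1 of 13 by class.
- Amiodarone: 0 of 13.
- Furadantine-type antibiotics: 0 of 13.
- So 1 of the 3 drug groups is covered and 2 are not.

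Even for bleomycin, criterion 2 is justified by wound healing. It catches the drug without being written to implement the lung-toxicity rule.

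**Does other text close the gap?** Section 5.2 adds no medication restriction. It concerns care during follow-up, so it is weak evidence about entry, but it certainly does not supply the missing criterion. Section 12.1h refers to attachment D1, which is not shown. Section 4.3 does not send a screener to it.

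**Comparison within the risk analysis.** The pregnancy exclusion in 12.1g matches criterion 6 of 4.3. The drug exclusion in 12.1h has no such match for two of its three groups.

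**Chance of exposure.** With 68 patients planned per group in each stage, first-stage allocation appears to be equal. A patient wrongly admitted in that stage would then have a 3/4 = 75% chance of allocation to an HBOT arm.

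**The case against.** The strongest reply is that this is an omission and not a contradiction. Section 4.3 does not claim to be exhaustive, nor does it say that amiodarone users may enter. Read as a whole, the protocol gives one answer: they are excluded. That reading is possible, but it depends on every site combining a numbered exclusion list with a sentence in chapter 12 to which the list does not refer. A site that follows 4.3 as written would admit these patients.

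The second reply is that the hazard is small at the trial's doses. Section 12.1h ties it to high oxygen doses. Section 12.1e describes prolonged very high dosing as the cause of pulmonary oxygen toxicity and says "The doses used in this study are much lower". Section 12.1j provides that "When a patient shows signs of pulmonary toxicity or has an epileptic attack, the treatment will be immediately stopped". This stands as a limit on the size of the hazard. It does not settle eligibility, because 12.1h excludes these patients despite those dose statements. The stopping rule also acts only after signs have appeared, and 12.1j acknowledges that no direct antidote exists.

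The third reply is that nothing shows how sites actually screen. The eligibility form and attachment D1 are not available, and either might carry the drug rule. This is fair, and it is why the consequence is stated as something that could happen. It does not remove the mismatch between the two sections.

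Finally, the count of criteria measures coverage of a list, not patients or bias. That is also correct, and no effect on the trial's estimates is claimed.

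**Conclusion.** The concern holds. Section 12.1h states a safety-based exclusion that section 4.3 does not contain for two of the three drug groups it names: 0 of 13 criteria cover amiodarone, and 0 of 13 cover furadantine-type antibiotics. Bleomycin is covered, but only through the chemotherapy criterion.

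The finding rests on the text of sections 4.2, 4.3, 5.2 and 12.1 and needs no outside figures. The 75% exposure figure assumes equal allocation. The protocol gives no frequency of use of these drugs, so the number of patients who might be admitted is unknown, and it is not claimed that harm will follow.

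This should be fixed because it concerns a safety rule at entry. It does not threaten the primary comparison.

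**What to change.** Add one exclusion criterion to section 4.3: current use of bleomycin, amiodarone, or furadantine and similar antibiotics. Name the antibiotics meant by the last phrase so that sites apply it in the same way. Make sure the pre-randomisation screening form carries the same item.

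If the clinical team judges the exclusion unnecessary at 90–120 minutes and 2.2–2.5 ATA, correct the sentence in 12.1h instead and give the reason there. Either way, both sections should state the same rule. The same amendment could usefully say what to do if one of these drugs is started while a patient is receiving HBOT.

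The cost is one line in 4.3 and one on the screening form, or one corrected sentence in 12.1h, plus a sentence if the rule for drugs started during HBOT is added. Endpoints, sample size and analysis do not change.

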#### i. Predictability of effect

There is no biomarker to predict the effect of HBOT. A forefoot Transcutaneous PO2 measurement could be used to predict the changes of successful treatment (Fife 2002).

j. Can effects be managed?

There is no direct antidote or antagonist. When a patient shows signs of pulmonary toxicity or has an epileptic attack, the treatment will be immediately stopped. For barotrauma an ENT specialist will be consulted, who might place eardrum tubes if necessary.

## **12.2 Synthesis**

HBOT is considered a cumbersome but low risk therapy. It has been implemented for a variety of indications and is routinely used, also for the treatment of (ischemic) DFUs. The risk of oxygen intoxication is minimised by using a well-known safe treatment window.

